15.5 Treatment of missing data

The primary analysis will use all available data with no imputation for missing data.

Sensitivity analyses to assess the potential impact of missing data on the study conclusions will be conducted.

15.6 Analysis of secondary clinical outcomes

Secondary clinical outcomes include duration of mechanical ventilation, ICU length of stay, hospital length of stay and ICU mortality.

Duration outcomes will be analysed as the number of days alive and free of outcome (e.g. days alive and free of mechanical ventilation or days alive and out of ICU) up to Day 90.

No adjusted or subgroup analyses of these outcomes will be performed.

Mechanical ventilation is only expected to occur while in ICU. Therefore, once discharged from ICU, patients will be assumed to be free of mechanical ventilation. Similarly, once discharged from hospital, patients will be assumed to be alive up to Day 90.

ICU mortality will be analysed in the same way as hospital mortality.

15.7 Analysis of microbiology and safety outcomes

15.7.1 Microbiology outcomes

- 1. new antibiotic resistant organism,
- 2. new bloodstream infections and
- 3. new *Clostridioides difficile* infections.

Proportions of patients with at least one event (e.g. one new bloodstream infection) will be compared between treatment arms using an analysis at the cluster-period level.

Linear regression will be used to model the proportion of events in each cluster-period.

15.8 Adverse events

Expected SAEs will be summarised as the number and proportion of patients experiencing at least one event, overall and by category the total number of events will be reported.

Proportions of patients with at least one SAEs and proportion of patients' dead will be compared between treatment arms using an analysis at the cluster-period level.

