10.3 Suspected Unexpected Serious Adverse Reactions (SUSARs)

A serious adverse drug reaction whose nature, severity, specificity, or outcome is not consistent with the term or description used in the product information, should be considered unexpected. These will also be reported to the coordinating centre within 24-hours of participating site study staff becoming aware of the occurrence.

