11.6 Serious and Unexpected Adverse Drug Reaction (SUADR)

SUADRs are SADR that are unexpected, where severity of which is not consistent with the applicable product information of each component of the paste and suspension.

All SUADRs will have expedited reporting to regulatory agencies following ICH-GCP and local regulatory requirements.

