11.7.2 Expectedness

Events are classified as unforeseen or unexpected if the nature, severity or frequency is not consistent with the risk information set out in the product information or label of each component of the paste and suspension.

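### Section 15.8 limits the descriptive SAE summary to expected events, while the next sentence compares arms on all SAEs, so unexpected serious reactions drop out of the summary and the two outputs need not agree

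*Protocol*

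**What the plan says.** Section 15.8 describes two safety outputs, one after the other. The first is descriptive: "Expected SAEs will be summarised as the number and proportion of patients experiencing at least one event". The same sentence then runs on, without clear punctuation, to "overall and by category the total number of events will be reported". The second is the formal comparison: "Proportions of patients with at least one SAEs and proportion of patients' dead will be compared between treatment arms". It is done at cluster-period level and does not mention expectedness.

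Elsewhere the protocol treats expectedness as a classification:

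- Section 10.3 (Australia) defines the unexpected class as "A serious adverse drug reaction whose nature, severity, specificity, or outcome is not consistent with the term or description used in the product information".
- Section 11.6 (Canada/UK) says "SUADRs are SADR that are unexpected".
- Section 11.7.2 says "Events are classified as unforeseen or unexpected if the nature, severity or frequency is not consistent with the risk information" in the product information or label of the components.

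Unexpected serious reactions are collected. Sections 10.3 and 10.4 require them to be reported to the coordinating centre with a minimum content. Section 11.7.5 puts related adverse events on the CRF with no expectedness filter.

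**The concern.** One short section uses two different sets of SAEs. The category summary is where a reader learns which serious harms occurred. As worded, it covers only reactions the product information already describes and leaves out those that would be new information about the paste and suspension. The comparison would count a patient whose only event was a SUSAR, but would not show what the event was. No other section of the protocol specifies a tabulation of unexpected serious reactions.

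Two consequences follow. The patient counts from the two sentences may fail to reconcile, with no explanation in the text. And membership of the summary depends on a classification that the protocol words differently in different places, although section 15.2.4 plans to merge the two regional databases.

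**Working it through.** The plan gives no figure here, so the check is logical.

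**Step 1: the two event sets.** Let E be the reported SAEs classed as expected and U those classed as unexpected. The classes are exclusive under sections 10.3, 11.6 and 11.7.2.

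- Descriptive summary (first sentence of 15.8): patients with an event in E.
- Between-arm comparison (second sentence): patients with an event in E or U.
- Difference in patient counts: patients with an event in U and none in E.

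The event sets differ as soon as one unexpected SAE occurs. The patient counts differ as soon as one patient has only unexpected SAEs.

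**Step 2: literal application to three illustrative records.** These are made up to show how the rule works and are not estimates.

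| Record | In the summary | In the comparison | Events if total is restricted | Events if total is unrestricted |
|---|---|---|---|---|
| One expected SAE | 1 | 1 | 1 | 1 |
| One unexpected SAE | 0 | 1 | 0 | 1 |
| One expected and one unexpected SAE | 1 | 1 | 1 | 2 |
| Sum | 2 | 3 | 2 | 4 |

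The summary shows 2 patients and the comparison 3. The category breakdown of patients reflects only the 2 expected events. In the third record the patient is counted in both outputs, but the unexpected event's category is missing.

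**Step 3: the event-total clause.** It can be read as governed by the sentence's opening subject (restricted, total 2) or as a clause with its own subject and verb (unrestricted, total 4). Under the second reading the total is complete, but it sits beside patient counts drawn from a smaller set.

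**Step 4: could *Expected* mean something else?** It might have meant events anticipated in this ICU population. The protocol has no list of such events, and its only defined use of the term is consistency with product information.

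**Step 5: is the class itself stable?** Section 10.3 uses nature, severity, specificity or outcome. Section 11.6 mentions severity. Section 11.7.2 uses nature, severity or frequency. A listed reaction that is unusual only in its frequency is unexpected under 11.7.2, but frequency is not a criterion in 10.3. Sections 10.6, 11.10 and 11.13 make every *C. difficile* infection a reportable SAE without saying whether it is expected, so whether these cases enter the summary is undetermined.

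**The case against.** The strongest reply is that this is one stray word in a garbled sentence. The only formal safety analysis is unrestricted and counts unexpected events. Oversight does not depend on 15.8: adverse reactions enter a safety database monitored by the management committee (10.1), the DSMC reviews all adverse reactions (10.5), and unexpected serious reactions are expedited (10.3, 11.6, 11.10 to 11.13). Section 15.2 leaves mock tables to a separate statistical analysis plan, which may list these events. All of this stands, and it confines the defect to the descriptive summary.

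It does not remove the defect. The point is not a missing table layout but a restriction that the protocol states and does not carry into its next sentence. An analysis plan that follows the wording inherits the restriction; one that summarises all SAEs departs from the wording.

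Some stronger readings are tempting but not supported:

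- *That the trial's safety counts exclude every unexpected reaction.* The protocol does not say that unexpected SAEs will go unsummarised, and the comparison includes them.
- *That the event total is understated by some percentage.* This needs the restricted reading of an ambiguous clause and a share of unexpected SAEs, which the documents do not give.
- *That the trial's stated aim is undermined.* The harm named in section 4.1 is antibiotic resistance, which sections 15.7.1 and 15.9 analyse separately. *C. difficile* infection also has its own comparison in 15.7.1.

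**Conclusion.** The point holds as a minor defect in safety reporting. As written, the descriptive patient counts and category breakdown in section 15.8 leave out SUSARs and SUADRs, and they will not match the between-arm comparison whenever a patient's only SAE is unexpected. Whether event totals are also restricted cannot be settled from the text. The primary and secondary outcomes, the between-arm SAE comparison, expedited reporting and DSMC review are unaffected.

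The size cannot be stated. It is zero if no unexpected SAE is reported, and otherwise depends on how many are and in which patients. The conclusion assumes that *Expected* carries the protocol's own defined meaning and that 15.8 is applied as worded. A drafting slip is plausible, which makes correction easier but no less necessary.

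**What to change.** Delete *Expected* from the first sentence of section 15.8 and repair its punctuation. It should then say that all reported SAEs are summarised by arm, overall and by category, as patients affected and as total events, with expectedness shown as a breakdown. State that the same event set is the numerator of the between-arm comparison and that reported *C. difficile* infections belong to it. SUSARs and SUADRs are subsets of serious adverse drug reactions, so the wording should not list them as additional items that could be counted twice.

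The cost is one sentence and a breakdown row, using data already collected under sections 10 and 11. The change only aligns the summary with the comparison. Control patients receive no study-specific intervention (7.3), so they cannot contribute study-drug reactions. That limit on interpreting the comparison remains either way.

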7.3 Control group

When the ICU is allocated to standard care (control) the same group of patients will be identified according to the inclusion and exclusion criteria above and will be followed up in the same way to the primary and secondary endpoints above. Patients will receive all usual infection control measures but will receive no study-specific interventions.

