9.2 Canada/UK (actual/indicative timelines)

Date	Project Milestone
July 2015 – December 2018	Start-up phase; including site feasibility and selection, and agreement by sites to follow study protocols (intensive care and infectious diseases)
August 2016	Protocol finalised
June 2019	Case Report Form (CRF) and other study documents finalised
May 2019	All ethics and other regulatory requirements met
May 2019	3-month pre-trial data collection period (surveillance ecology); site randomisation and initiation commenced
September 2019	First trial recruitment period (SDD or control) and 3-month surveillance ecology data collection period during recruitment period commenced
March 2020	Suspension of recruitment due to COVID-19 at all sites
May 2020	Potential restart after COVID-19 commenced
March 2021	Start of 3-month inter-period data collection (surveillance ecology) and site initiation for crossover
June 2021	Start of second trial recruitment period (control or SDD after crossover) and 3-month surveillance ecology data collection period during recruitment period
July 2022	Start of 3-month post-trial data collection period (surveillance ecology)
December 2022	Potential completion of post-trial collection period (surveillance ecology) final site

June - December 2023	Database lock, analysis and publication of Canada/UK dataset. This will be followed by merger with Australian database, analysis and publication of combined primary (mortality) and secondary (ecology) endpoints of combined dataset, subject to funding
----------------------	--

10 Safety monitoring and reporting : Australia

Critically ill patients in the ICU have a number of perturbations in laboratory values, signs and symptoms due to the severity of the underlying disease and the impact of standard medical therapies. These will not necessarily constitute an adverse event or serious adverse event unless they are considered to be related to study treatment or a concern in the principal investigator's clinical judgement.

In this study, reporting of adverse events will be restricted to events that are considered to be related to study treatment (possibly, probably or definitely).

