10.2 Serious Adverse Drug Reactions (SADRs)

Serious adverse *events* are defined as any untoward medical occurrence that meets one of more of the following criteria:

- 1. Results in death
- 2. Is life-threatening
- 3. Requires inpatient hospitalisation or prolongation of existing hospitalisation
- 4. Results in persistent or significant disability/incapacity
- 5. Is a congenital anomaly/birth defect

The classification of 'serious adverse event' is not related to the assessment of the severity of the adverse event. An event that is mild in severity may be classified as a serious adverse event based on the above criteria. Given that critically ill patients are likely to experience any of the above listed criteria in the course of their ICU admission, only serious events that are thought to be study treatment related will be reported.

Serious adverse drug reactions should be reported to the coordinating centre within 24-hours of participating site study staff becoming aware of the occurrence. A member of the coordinating centre will be on call 24-hours a day via mobile phone for out of 'business hours' reporting.

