10.6 Antibiotic Resistant Organism (ARO) outbreaks

An ARO outbreak is defined by the need for any new infection control interventions that are deemed (by the site investigator) to be directed specifically to outbreak containment. These must be reported to study Management Committee and will be assessed by the DSMC. Usual study procedures should continue while any outbreak is being assessed.

As ARO rates are being assessed as an endpoint of the trial, we do not propose to change the clinical intervention in the event of an observed increase in multi-resistant infections in a participating unit during the trial periods or to discontinue the SDD intervention.

Study sites will decide on the appropriate clinical management as determined by the clinical team and infection control staff of that unit. The study sites will be actively encouraged to resume normal trial conduct after control of the situation.

All cases of *Clostridioides difficile* infection will be reported as serious adverse events.

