11.7.5 Adverse Event Recording

Adverse events that are assessed and determined **not** to be related to the investigational product will not be recorded and reported.

In this study, recording and reporting of adverse events will be restricted to events that are assessed by the site investigator or delegated sub-investigators to be related to investigational product (i.e. possibly, probably or definitely related).

Investigations into potential adverse events should be done during each contact with a participant. Investigations may be done through specific questioning and, as appropriate, by examination. Information on all adverse events should be recorded promptly in the source document e.g. medical chart, progress notes, and assessed by the site investigator or delegated sub-investigators in a timely manner allowing sufficient time to meet required reporting timelines for AEs if needed. Only AEs that are related to the investigational product, regardless of seriousness, will be recorded on the study CRFs (e.g. adverse event

CRFs). Adverse event CRFs should be completed using source documents by a delegated research team member in a timely manner/within 15 days of site awareness. All clearly related signs, symptoms, and abnormal diagnostic procedures should be recorded in the source document, though should be grouped under one diagnosis. Each diagnosed adverse event should then be categorized in accordance with Medical Dictionary for Regulatory Activities (MedDRA) classifications.

If the site investigator or delegated sub-investigator is unsure about whether the event is caused by or related to the investigational product, then the event will be handled as "related" to the study drug for reporting purposes of the trial. If the causality assessment is "unknown but not related" to the investigational product, this should be clearly documented in the source documents.

The following are not considered AEs and therefore do not require recording:

- 1. Pre-existing diseases or conditions identified and recorded at screening/baseline unless, at the discretion of the site investigator, the disease or condition worsens in severity or frequency
- 2. At the discretion of the site investigator, events considered likely manifestations of the underlying disease or that commonly occur in the study population independent of investigational product exposure
- 3. Elective medical or surgical procedures.

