11.8 Reporting of SAEs and Unanticipated Events

Serious adverse events and unanticipated events that are assessed and determined **not** to be related to the investigational product **will not** be recorded and reported.

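### Section 15.8 compares SAE proportions between arms, but apart from C. difficile an SAE counts only if attributed to a study drug that control patients never receive

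*Protocol*

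**What the plan says.** **The planned comparison.** Protocol Section 15.8: "Proportions of patients with at least one SAEs and proportion of patients' dead will be compared between treatment arms", analysed at cluster-period level. Section 15.2.3 uses the intention-to-treat set for safety, so both arms enter.

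**What counts as a reportable event, Australia.** The introduction to Section 10 says that "reporting of adverse events will be restricted to events that are considered to be related to study treatment". Section 10.2 applies the same limit to serious events: "only serious events that are thought to be study treatment related will be reported".

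**What is recorded, Canada/UK.** Section 11.7.5: "Only AEs that are related to the investigational product, regardless of seriousness, will be recorded on the study CRFs". Section 11.8 opens with "Serious adverse events and unanticipated events that are assessed and determined" and goes on to say that, where the determination is unrelated, such events are neither recorded nor reported. Under Sections 11.7.1 and 11.7.5, an event of uncertain causality is treated as related.

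**The control arm.** Section 7.3: control patients "will receive no study-specific interventions". Section 7.6 says the trial is unblinded.

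**The exception.** Section 10.6 says that every case of C. difficile "infection will be reported as serious adverse events". Sections 11.10 and 11.13 make the same provision for Canada/UK.

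**The concern.** A between-arm comparison of event proportions is interpretable when an event has the same chance of being counted in either arm. Here the rule for counting depends on the arm. A serious event in an SDD patient is counted if the investigator thinks the drug may have caused it. The same event in a control patient has no study drug to be related to, so it is not counted unless it is C. difficile infection.

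At stake is how the safety result reads. An SAE comparison by arm looks like comparative safety evidence, and this one can only be pushed in one direction, against SDD, by the attribution step. It also cannot detect a real rise or fall in serious events that nobody attributes to SDD and that fall outside the outcomes collected in both arms. Because the protocol fixes the comparison, a statistical analysis plan that follows it inherits the problem.

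**Working it through.** The protocol states no SAE rate, C. difficile rate or SAE power, so there is no figure to reproduce. The check sets the rules side by side and then works out what the comparison estimates.

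**Step 1. Which SAEs can be counted in each arm**

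| Event type | SDD arm | Control arm | Source |
|---|---|---|---|
| C. difficile infection | All cases | All cases | 10.6, 11.10, 11.13 |
| Other serious event judged related to study drug | Counted | Cannot arise | 10, 10.2, 11.7.5, 7.3 |
| Other serious event of uncertain causality (Canada/UK) | Counted as related | No counterpart | 11.7.1, 11.7.5 |
| Other serious event judged unrelated | Not counted | Not counted | 10.2, 11.8 |

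The control-arm data list in Section 8.4 covers ventilation, antibiotics, C. difficile, cultures, resistant organisms, discharge and death. It contains no general SAE collection that would fill the gap.

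**Step 2. What the comparison estimates**

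Let c be the control proportion with C. difficile, c′ the SDD proportion with C. difficile, and r the SDD proportion with an attributed SAE but no C. difficile.

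- Control proportion = c
- SDD proportion = c′ + r
- Difference = (c′ − c) + r

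Section 15.7.1 already compares new C. difficile infections between arms, so what the SAE test adds is essentially r, a quantity defined in one arm only. With c′ = c the difference is r.

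**Step 3. Size, over an assumed range**

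The documents give neither c nor r, so both are assumptions. With c′ = c:

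- r = 0.25% gives an excess of 0.25 percentage points
- r = 0.5% gives 0.5 points
- r = 1% gives 1 point

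**Step 4. How often such an excess would be nominally significant (illustration only)**

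Inputs from Section 15.1: 150 patients per cluster-period, the planning table's 20 Australian clusters, ICC 0.01, inter-period correlation 0.005.

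- Patients per arm: 20 × 150 = 3000
- Design effect: 1 + (150 − 1) × 0.01 − 150 × 0.005 = 1.74
- Effective number per arm: 3000 / 1.74 = 1724

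As a check, the same design-effect formula applied to the mortality table in Section 15.1 (control 29%, two-sided 5%) gives 79.4% to 82.0% power for the seven tabulated differences, against the stated 80%.

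The chance of a significant excess is approximately Φ(r/SE − 1.96), with SE² = [c(1 − c) + (c + r)(1 − c − r)] / 1724. For c = 0 and r = 0.5%: SE = √(0.005 × 0.995 / 1724) = 0.0017, r/SE = 2.94, and Φ(0.98) = 84%.

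| Assumed c | r = 0.25% | r = 0.5% | r = 1% |
|---|---|---|---|
| 0 | 55% | 84% | 99% |
| 0.5% | 15% | 40% | 84% |
| 1% | 10% | 26% | 68% |
| 2% | 7% | 17% | 47% |

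For two arms with the same underlying proportion, the rate in that direction would be 2.5%. These are normal approximations with few events, and they borrow correlations estimated for mortality, so only the pattern should be relied on. They are false-positive rates only to the extent that r consists of background events wrongly attributed to SDD.

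**The case against.** **Some of r is real harm.** A correctly attributed drug reaction cannot occur in a patient not given the drug, so its absence from the control arm is no artefact. This stands. A reader might infer that the whole difference is spurious; the documents do not support that. What they do support is that the comparison cannot separate true reactions from misattributed background events, and that attribution is made with the arm known.

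**The control rate is not zero.** A reader might infer that the control SAE rate is nil or near nil by construction. It is not: all C. difficile cases count in both arms, and the protocol gives no rate for them.

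**Symmetric comparisons are already planned.** Section 15.8 compares deaths, Section 15.7.1 compares C. difficile, bloodstream infection and resistant organisms, and Section 15.6 analyses ICU mortality and the duration outcomes. This stands too. The blind spot is limited to serious events outside those outcomes.

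**The related-only rule is disclosed and reasoned.** Sections 10 and 10.2 explain that critically ill patients commonly meet seriousness criteria anyway. That is a defensible choice about collection. It does not justify comparing the result between arms.

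**Section 11.13 might be read as wider.** Its item on SAEs other than death and immediately life-threatening events does not repeat the relatedness condition. Section 11.8, however, excludes unrelated SAEs outright, and nothing comparable exists for Australia.

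**Presentation is for the analysis plan.** The protocol does not promise a p-value or interval for SAEs. True, but it does commit to a modelled between-arm comparison, and changing the presentation would not make the counting rule symmetric.

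**Conclusion.** The point holds. As written, Section 15.8 compares C. difficile alone in the control arm with C. difficile plus drug-attributed SAEs in the SDD arm. No other section resolves this, whether by collecting other SAEs in controls or by limiting the comparison to events counted in both arms. In Australia the limit is on reporting and in Canada/UK on recording; the effect on the comparison is the same.

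The size cannot be determined from the protocol. On the assumption of equal C. difficile rates, an attributed-SAE rate between 0.25% and 1% appears as an excess of 0.25 to 1 percentage points on SDD. How much of that would be true reaction and how much misattribution is unknown.

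Severity is moderate. The SAE proportion is neither the primary outcome nor a listed secondary outcome. The comparison of deaths in the same sentence is sound, because death is collected in both arms. The primary, secondary and ecology analyses are unaffected.

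**What to change.** In Section 15.8:

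1. Remove the between-arm test of the proportion of patients with at least one SAE.
2. Summarise drug-related SAEs descriptively, in the SDD arm only.
3. Base comparative safety on the events collected in both arms and already compared in Sections 15.7 and 15.8: death, C. difficile infection, bloodstream infection and resistant organisms.
4. Wherever safety is reported, state that other serious events were captured only when attributed to study drug and so are not compared between arms.

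The cost is a few sentences in Section 15.8 and matching changes to the table shells, with no new data. The downside is that the report carries no overall SAE comparison.
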